5.2 Exclusion Criteria

Participants are excluded from the study if any of the following criteria apply:

Medical Conditions

1. Participants determined ineligible to participate in this study at the discretion of the Principal Investigator (or delegated investigators).
2. Hypersensitivity to venous puncture
3. Known hypersensitivity to ingredients of study interventions or Biguanides, or having other clinically relevant hypersensitivities
4. Type I diabetes mellitus, lactic acidosis, acute or chronic metabolic acidosis including diabetic ketoacidosis, with or without coma; diabetic pre-coma, pre-diabetes
5. Patients with renal impairment (eGFR with MDRD < 80 mL/min/1.73m² – calculations according to Modification of Diet in Renal Disease (MDRD) formula). Patient presenting with acute conditions with the potential to alter renal function such as dehydration, severe infection, cardiovascular collapse (shock), acute myocardial infarction, and septicemia

6. Participants with acute and unstable heart failure
7. Participants with severe infection or severe traumatic general disorder
8. Participants who are scheduled to undergo surgical procedures
9. Participants with malnutrition, inanition, pituitary dysfunction or adrenal function failure
10. Participants with hepatic dysfunction, acute or chronic disease which may cause tissue hypoxia such as respiratory failure, acute myocardial infarction, shock and GI disorder such as excessive alcohol intake, hydration, diarrhea, vomiting etc.
11. Participants undergoing intravascular administration of iodinated contrast materials in radio diagnostic examinations (for example, intravenous urogram, intravenous cholangiography, angiography, and computed tomography (CT) scans with intravascular contrast materials etc.)

Prior/Concomitant Therapy

12. Participants who took drugs that significantly induce (e.g., barbiturate) or inhibit drug metabolism enzymes, and those drugs that may alter metformin pK, most importantly OCT1/2 inhibitors and inducers, within 30 days prior to screening.
13. Use of a concomitant drug. However, any medications that are considered necessary for participant's welfare and will not interfere with the trial medication may be given at the discretion of the Investigator. For the detail of prohibited medicines, see Section 6.5.3 (Prohibited Medicines).
14. Use of any medication that may affect the outcome of the study within 10 days prior to screening and during study conduct

Prior/Concurrent Clinical Study Experience

15. Participation in another bioequivalence or other clinical studies where the last administration of previous study medication was within 6 months, before the first drug administration in this study

Other Exclusions

16. Donation of whole blood or loss (≥ 400 mL) within 2 months, plasma donation or apheresis within 2 weeks prior to first drug administration
17. History of regular alcohol drinking within 6 months prior to screening as shown below
 - For females, > 14 cups/week
 - For males, > 21 cups/week

(1 cup: Soju 50 mL, Liquor 30 mL, Beer 250 mL)
18. Excessive consumption of xanthine-containing food or beverages (> 5 cups of coffee a day or equivalent) or inability to stop consuming caffeine, from 48 hours prior to drug administration until collection of last PK sample in each period (hour 32 [H32]).

19. Intake of grapefruit, orange, cranberry or juices of these three fruits, from 48 hours prior to drug administration until collection of last PK sample in each period (hour 32 [H32]).
20. Inability to communicate or cooperate with the Investigator (e.g., language problem, illiterates, poor mental status) or to comply with the requirement of the entire trial, including dietary restrictions.
21. Non-acceptance of study high-fat breakfast for participant included in the fed group (e.g., vegetarians, vegans and participants who follow special diets).
22. Legal incapacity or limited legal capacity.
23. Participants kept in detention.

5.3 Lifestyle Considerations

5.3.1 Meals and Dietary Restrictions

(1) Part 1: Fasted state (both periods)

- Refrain from all food and beverages (except water) for at least 4 hours prior to clinical laboratory tests (except for tests on Day-1).
- Refrain from all food and beverages (except water) for at least 10 hours before and 4 hours after dosing.
- Refrain from water for 1 hour before and after dosing except 150 mL water for administration.
- Lunch is served after blood collection at 4 hours after dosing.
- Dinner is served around 06:00 pm on Day -1 after blood collection, and at 10 hours after dosing.

(2) Part 2: Fed state (both periods)

- Refrain from all food and beverages (except water) for at least 4 hours prior to clinical laboratory tests (except for tests on Day-1).
- Refrain from all food and beverages (except water and milk or juice in the course of high-fat meal) for at least 10 hours before high-fat meal intake and 4 hours after dosing.
- Refrain from water for 1 hour before and after dosing.
- From around 7:30 am on the day of the study, take all of breakfast (more than 900 Kcal, more than 35% fat) without leaving any food at 1-minute interval in the order of random assignment number, and the meal time should be completed within 20 minutes.
- Lunch is served after blood collection at 4 hours after dosing.
- Dinner is served around 06:00 pm on Day -1 after blood collection, and at 10 hours after dosing.

5.3.2 Caffeine, Alcohol, and Tobacco

- During each dosing session, participants will abstain from ingesting xanthine-containing beverages (e.g., coffee, tea, cola drinks, and chocolate) from 48 hours before the start of dosing until after collection of the final pharmacokinetic (PK) and/or pharmacodynamic sample.
- During each dosing session, participants will abstain from alcohol for 24 hours before the start of dosing until after collection of the final PK and/or pharmacodynamic sample.
- Use of tobacco products will not be allowed from at least three months before study entry until after the final follow-up visit.

5.3.3 Activity

- Participants will abstain from strenuous exercise for 48 hours before admission to the Clinical Facility for each Period. Participants may participate in light recreational activities (e.g., watching television or reading).
- Participants should not lie down for at least 2 hours post administration of study interventions in a sitting position and should maintain similar posture and behavior to minimize the effect on blood flow velocity and motility of gastro intestines.
- Because metformin may cause very rarely severe lactic acidosis, participants have to stay at clinical site for 32h after each administration though it is for pharmacokinetic samplings. Additionally, if any of the following symptoms or signs comes out, it should be notified to the investigators immediately, and the investigators should check for the abnormalities through careful monitoring. Hypoglycemia has not been seen with metformin doses of up to 85 g, although lactic acidosis has occurred in such circumstances. High overdose or concomitant risks of metformin may lead to lactic acidosis. Lactic acidosis is a medical emergency and must be treated in hospital. The most effective method to remove lactate and metformin is hemodialysis.
 - Lactic acidosis: Unexplained hyperventilation, myalgia, malaise, unusual somnolence, or other nonspecific symptoms

5.4 Screen Failures

Individuals who do not meet the criteria for participation in this study (screen failure) may be re-screened for Clinical laboratory test, 12-lead ECG, etc.. If clinical laboratory test results are out of reference range, additional visits may be requested to conduct a re-test or further examination at the discretion of the Principal Investigator (or the delegated investigators). If the test result is judged to be a transient change due to lifestyle (specific diet, drinking, exercise, night shift, etc.), it is possible to re-test participants once after correction of lifestyle

at the discretion of the Principal Investigator (or delegated investigators). If re-test is performed, the inclusion criteria are confirmed based on the last result value. Re-screened participants will retain their initially assigned screening numbers.

6 Study Intervention(s)

Study intervention is any investigational intervention(s), marketed product(s), placebo, or medical device(s) intended to be administered to a study participant per the study protocol.

6.1 Study Intervention(s) Administration

Study Interventions		
	Test Drug	Reference Drug
Study Intervention Name:	500 mg Glucophage® XR Reduced Mass tablet	500 mg Glucophage® XR tablet
Dose Formulation:	Tablet	Tablet
Unit Dose Strength(s)/Dosage Level(s):	Metformin hydrochloride 500 mg	Metformin hydrochloride 500 mg
Physical Description	White to off-white, round, biconvex tablet debossed with “500” on one side	White to off-white, capsule-shaped, biconvex tablet engraved “500” on one side and “XR” on the other
Route of Administration:	p.o.	p.o.
Dosing Instructions:	Metformin tablets will be administered as a single dose of 500 mg either as a Glucophage XR Reduced Mass tablet (Test drug) or Glucophage XR tablet (Reference drug) in fasted or fed condition as described in Section 5.3.1 (Meals and Dietary Restrictions).	
Supplier/Manufacturer:	Manufacturer of (commercial) drug product: Merck Sante s.a.s – Semoy (France) Manufacturer of Study Intervention: Merck Healthcare KGaA, Darmstadt (Germany) Both the finished product of Test drug and Reference drug are manufactured at the same manufacturing site (Merck Sante s.a.s – Semoy (France))	

Storage Condition:	In airtight container not above 30°C
Packaging and Labeling	The study interventions shall be manufactured by the Sponsor in accordance with all applicable regulatory requirements and Good Manufacturing Practice Guidelines and will be supplied to Clinical Facility as QP (Qualified Person) released and labeled study intervention (unblinded labeled blister containing 15 tablets each). Labeling will be done on the blister in accordance with all applicable regulatory requirements and Good Manufacturing Practice Guidelines.
GCP Dispensing	Upon study intervention delivery, the PI delegated Clinical Trial Pharmacist for study intervention (hereinafter referred to as “the Clinical Trial Pharmacist”) checks the information (quantity and storage condition of study interventions) provided in the receipt form and enclosed documents. He/she then records the information in the study intervention logbook. The unopened carton is kept in the storage room as indicated. The Clinical Trial Pharmacist will generate the study intervention prescription codes so that the Investigator can prescribe the study intervention via the Electronic Medical Record (EMR). Detailed GCP Dispensing follows SOP of the Clinical Facility.

6.2 Study Intervention(s) Preparation, Handling, Storage, and Accountability

The Investigator, institution, or the head of the medical institution (where applicable) is responsible for study intervention accountability, reconciliation, and record maintenance (i.e., receipt, reconciliation, and final disposition records). For this study, the PI will delegate these responsibilities to the Clinical Trial Pharmacist for study intervention (hereinafter referred to as “the Clinical Trial Pharmacist”).

- Upon receipt of the study intervention(s), the Investigator or designee (i.e., Clinical Trial Pharmacist) must confirm appropriate temperature conditions have been maintained during transit and any discrepancies are reported and resolved before use. Also, the responsible person will check for accurate delivery and acknowledge receipt by signing or initialing and dating the appropriate document and returning it to the location specified. A copy will be archived for the Investigator Site File.
- Only participants enrolled in the study may receive study intervention(s) and only authorized site staff may dispense it. All study intervention(s) must be stored in a secure, environmentally controlled, and monitored (manual or automated) area, in accordance

with the labeled storage conditions, and with access limited to the Investigator and authorized site staff.

- Dispensing will be recorded on the appropriate accountability forms so that accurate records will be available for verification at each monitoring visit.
- Study intervention(s) accountability records at the study site will include the following:
 - Confirmation of receipt, in good condition and in the defined temperature range.
 - The inventory provided for the clinical study and prepared at the site.
 - The dose(s) each participant used during the study.
 - The disposition (including return, if applicable) of any unused study intervention(s).
 - Dates, quantities, batch numbers, container numbers, expiry dates and the participant numbers.
- The Investigator site will maintain records, which adequately documents that participants were provided the doses specified in this protocol, and all study intervention(s) provided were fully reconciled.
- Unused study intervention(s) must not be discarded or used for any purpose other than the present study. No study intervention that is dispensed to a participant may be re-dispensed to a different participant.
- A Study Monitor will periodically collect the study intervention(s) accountability forms.
- Further guidance and information for the final disposition of unused study intervention(s) are provided in the SOP of Clinical Facility.

6.3 Measures to Minimize Bias: Study Intervention Assignment and Blinding

6.3.1 Study Intervention Assignment

Block Randomization Method at the Clinical Facility	The Principal Investigator (or delegated investigators) uses a block randomization method in accordance with the Clinical Facility SOP to determine which product, Test Drug or Reference Drug, would be administered in Part 1 and Part 2 respectively, and based on this, prescribes the study interventions for bioequivalence study. According to the prescription, the Clinical Trial Pharmacist prepares the study interventions for Part 1 and Part 2 in accordance with the Clinical Facility SOP. The Principal Investigator (or delegated investigators) keeps records of the prescription.
--	---

Participant identifier & Assignment to treatment sequence	
For Part 1 (Fasted state) and Part 2 (Fed state), screening number in the form of SXXX (e.g. 'S301, S302, S303 ...' if it is for Part 1 and 'S401, S402, S403 ...' if it is for Part 2) is given to the applicants who visited the Clinical Facility and agreed the informed consent in writing. The screening number will be used to identify the participants for the whole duration of the bioequivalence study.
 
One day (Day -1) prior to administration of study intervention of Period 1, each participant is given a participant number according to the order of obtainment of the Informed Consent and the Sequence is randomly assigned to each of Part 1 (Fasted state) and Part 2 (Fed state). Randomization is done using Excel or SAS programs, and a total of 82 participants (Part 1: 48 participants, Part 2: 34 participants) are randomly assigned to 2 Sequences (1 or 2) with 24 participants per Sequence in Part 1 and 2 Sequences (1 or 2) with 17 participants per Sequence in Part 2 in a 1:1 ratio.
 
Randomization number is given to the 48 participants if it is Part 1 (Fasted state) and to the 34 participants if it is Part 2, excluding the stand-by participants (waiting list), who satisfied the screening, inclusion/exclusion criteria and clinical laboratory tests. The randomization number is the number of the administration order of participants and its form is R1YY (e.g., R101, R102, R103, ..., R148) if it is Part 1 (Fasted state) and R2YY (e.g., R201, R202, R203, ..., R234) if it is Part 2 (Fed state). Participants who have been assigned a randomization number but dropped out before the first administration of Period 1 can be replaced with stand-by participants. When the participant is replaced, the stand-by participant will be assigned the drop-out's randomization number. However, participants will not be replaced after the first administration of Period 1.

--	--

6.3.2 Blinding

Blinding Method

Not applicable, this is an open-label study.

Assignment Method Retention

Not applicable, this is an open-label study.

Unblinding Clinical Studies for Sample Analysis of Special Data

This is an open-label study. However, the Analytical Facility will initially be blinded to prevent biases that might affect the result of sample analysis. The randomized sample code will be unblinded to the Analytical Facility only following the completion of sample analysis. Analytical Facility initiates statistical analysis after receiving the unblinded sample code from the Clinical Facility.

The samples from Part 1 (Fasted state) and Part 2 (Fed state) that are delivered to the Analytical Facility are blinded so that Information on administration of study intervention (Test or Reference, blood collection time, Period) are not known. Samples are randomized according to the SOP of Clinical Facility to assign sample codes to the samples.

- The blinded sample code should be indicated only on the sample or source data (Eppendorf tube, Box, Sample transfer related documents, etc.). Example of Eppendorf tube label is as follows.

Protocol No. CCI	Part 1 or CCI
Sampling time point, period and Participant number / PPD	
For Analysis or Back-up / AN or BU	

Information on blinded sample is not disclosed to the Analytical Facility until the concentration measurement is completed. Once the concentration analysis at the Analytical Facility is completed, the concentration of each sample from Part 1 (Fasted state) and Part 2 (Fed state) is informed to the Clinical Facility. After the Principal Investigator of Clinical Facility receives the concentration of each sample from Part 1 (Fasted state) and Part 2 (Fed state) from the Analytical Facility, he/she provides the blinded information on the sampling time and period to the Analytical Facility. After the Analytical Facility confirms the blinded information on the sampling time and period, the Analytical Facility performs Incurred Sample Reanalysis (ISR). After the Principal Investigator of Clinical Facility receives the ISR result from the Analytical Facility, he/she provides the blinded information on the sample code. After the Analytical Facility confirms the blinded information on the sample code, the sample code is unblinded.

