9.3 Populations for Analyses

The analysis populations are specified below. The final decision to exclude participants from any analysis population will be made during a data review meeting prior to database lock.

Analysis Set	Description
All Randomized	Demographic Information is evaluated for those participants who participate in the bioequivalence study (i.e., all participants who were randomized). However, the participants who were replaced by the stand-by participants before the first administration of study interventions will be excluded from the analysis.

Analysis Set	Description
Safety	Safety is evaluated for those participants who were administered at least one dose of the study interventions.
PK	Pharmacokinetics is evaluated for those participants whose pharmacokinetics evaluation is possible by the completion of all planned pharmacokinetics blood collection schedules according to the Protocol, who do not exhibit concentrations exceeding 5% of the maximum plasma concentration (C_{max}) of the drug in the pharmacokinetics sample of prior to dosing and who have valid primary endpoints for both treatments.

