9.4 Statistical Analyses

Details on the statistical analysis will be presented in the statistical analysis plan (SAP) that will be finalized prior to database lock.

The statistical analysis will not start until all data have been corrected and checked for plausibility and until all necessary coding and assessments have been completed.

All data will be evaluated as observed; no imputation method for missing values will be used.

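### Concentrations and treatment codes are released without waiting for SAP signature, the PK-set decision or database lock, so judgement-based exclusions may be settled with each participant's T/R knowable

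*Protocol*

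**What the plan says.** Protocol 6.3.2 sets the order in which the laboratory blind is lifted. When measurement is finished, "the concentration of each sample from Part 1 (Fasted state) and Part 2 (Fed state) is informed to the Clinical Facility". The investigator then returns sampling time and period to the laboratory, which runs ISR. Next, "After the Principal Investigator of Clinical Facility receives the ISR result from the Analytical Facility, he/she provides the blinded information on the sample code". A general statement in the same section says "The randomized sample code will be unblinded to the Analytical Facility only following the completion of sample analysis", and the start of the statistics is described as follows: "Analytical Facility initiates statistical analysis after receiving the unblinded sample code from the Clinical Facility".

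The trial is open-label, and Protocol 6.3.1 has the investigator prescribe the products and keep the prescription records.

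The deadlines for the analysis decisions are elsewhere:
- Protocol 9.3: "The final decision to exclude participants from any analysis population will be made during a data review meeting prior to database lock".
- Protocol 9.4: "Details on the statistical analysis will be presented in the statistical analysis plan (SAP) that will be finalized prior to database lock".
- Protocol 9.4.3.1 gives the plan for the PK analyses the same deadline, database lock.
- Protocol 9.4 also says: "The statistical analysis will not start until all data have been corrected and checked for plausibility". Coding and assessments must be complete as well.

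Two routes out of the PK analysis rest on judgement. Protocol Appendix 2 (Non-Compliance of Protocol) excludes, in principle, a participant whose non-compliance is held to affect interpretation significantly, and its list of reasons is expressly not exhaustive. SAP 6.3 leaves out a PK value considered biased by an unexpected event, with vomiting as the example.

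**The concern.** The laboratory blind is the only blind in the trial. It protects the measurement. It does not protect the later decision on whose measurements count, because nothing requires that decision to come before the results can be read by treatment. The investigator holds the allocation, so concentrations by participant and period are enough to work out T/R at the site, before ISR and before the code is released.

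At stake is the error rate of the primary conclusion. Each metric is judged by one 90% confidence interval, planned on 38 evaluable participants fasted and 22 fed. If the true ratio lies near a limit, removing one person with an unfavourable ratio can decide the outcome. The one-sided 5% level holds only if the set of participants is chosen without regard to their ratios.

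**Working it through.** **Order of events**

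| Step | Source | Tied to SAP signature, PK-set decision or lock? |
|---|---|---|
| Concentrations to the open-label site | Protocol 6.3.2 | No |
| Time and period to the laboratory, then ISR | Protocol 6.3.2 | No |
| Sample code to the Analytical Facility | Protocol 6.3.2 | No |
| Statistics start | Protocol 6.3.2 and 9.4 | After code receipt, and after data are clean and coded; lock not named |
| Final exclusions | Protocol 9.3 | Before lock; the meeting is not stated to be blinded |
| SAP and PK analysis plan | Protocol 9.4, 9.4.3.1 | Before lock |

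Nothing places the last two rows before the first.

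**Reproducing the plan's sample size (Protocol 9.2.2)**

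Inputs: GMR 0.95, one-sided alpha 0.05, limits 0.80 to 1.25, CV 25% with N = 38 (fasted), CV 18.7% with N = 22 (fed).

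Formulas: σ_w = √ln(1 + CV²); SE = σ_w·√(2/N); df = N − 2; exact power of the two one-sided tests.

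- Fasted: σ_w = √ln(1.0625) = 0.246; SE = 0.246 × √(2/38) = 0.0565; power 90.9%.
- Fed: σ_w = √ln(1 + 0.187²) = 0.185; SE = 0.185 × √(2/22) = 0.0559; power 90.6%.
- Dropout: 38/0.80 = 47.5, so 48; 22/0.65 = 33.8, so 34.

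The plan's figures reproduce.

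**What selection with ratios known could do**

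The setting is one metric in one part at true T/R = 0.80, where a bioequivalence finding is false. Each participant's log difference T − R is drawn from a normal distribution with mean ln 0.80 and SD σ_w·√2, half in each sequence. The 90% interval is compared with ln 0.80 and ln 1.25. If it fails, the eligible participant with the lowest T/R is removed and the interval recomputed. Each setting had at least 20,000 simulated trials.

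| Who may be removed | N = 38, CV 25% | N = 22, CV 18.7% |
|---|---|---|
| Nobody | 5% | 5% |
| Any one participant | 11% | 13% |
| Any two participants | 19% | 23% |
| One, if a random 20% are excludable | about 8% | about 8% |
| One, if a random 10% are excludable | about 7% | about 7% |

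The 10% and 20% shares are assumptions; the documents give no such figure. SAP 3.1 requires all 8 one-sided null hypotheses to be rejected (two metrics, two parts), which can only lower these rates.

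**At the planned ratio**

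At an estimated ratio of 0.95 the lower limit is exp(ln 0.95 − 1.688 × 0.0565) = 0.86 fasted and exp(ln 0.95 − 1.725 × 0.0559) = 0.86 fed, well above 0.80. Free removal of the worst participant then turns failure into success in about 5% (N = 38) or 6% (N = 22) of trials. With all 48 or 34 evaluable it does so in about 2.5% or 1.3%.

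**The case against.** The other side has a good case on several points.

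- **The statistics sentence is a restriction.** A reader might infer that 6.3.2 lets the statistics start on code receipt alone and so contradicts 9.4. It does not say that. Code receipt is a necessary condition, 9.4 adds clean and coded data, and both can hold together. Deleting the sentence would remove a limit.
- **The code does not go out when the assay ends.** Only the concentrations do. The code follows the return of time and period, ISR and the ISR result.
- **Who runs the statistics.** Protocol 6.3.2 has the Analytical Facility starting them and Appendix 2 assigns them to the CRO. That these are one organisation is an inference, because names are redacted. The point does not need it.
- **Most of the analysis is already fixed.** The protocol sets the metrics, ANOVA terms, interval and limits (9.1, 9.4.3.1), the AUC method (8.5), handling of values below quantification (section 9), no imputation (9.4) and no interim analysis (9.4.3.4). The PK set in 9.3 is largely objective. A reader might infer that the whole analysis is open to choice; it is not.
- **Free deletion is not allowed anywhere.** An exclusion needs a deviation or an event, and the most adverse participant need not have either.

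All of this stands and narrows the point. What remains are the two judgement-based exclusions, and a SAP whose content is not wholly dictated by the protocol: SAP 3.2 carries a second route to equivalence that Protocol 9.1 does not. Both are due only before lock, and 9.4 restrains running the analysis, not seeing the data.

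**Conclusion.** The concern holds as a gap in sequencing that is cheap to close. The stated order permits the PK set to be settled with each participant's T/R knowable at the site.

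A reader might infer that decisions were in fact made late. The documents do not support that. They give no dates for the end of the assay, code release or lock, and the SAP log shows version 2.0 adding only the blood sugar safety analysis.

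Nor should the 11% to 23% figures be read as a forecast or a ceiling. They assume a true ratio of exactly 0.80, one metric in one part, and unrestricted removal of one or two participants. With 10 to 20% of participants excludable and one removal, the rate is about 7 to 8% against 5%. The effect is smaller still when all metrics in both parts must pass, and it vanishes if the judgement-based exclusions are fixed before the concentrations are seen.

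**What to change.** In Protocol 6.3.2, 9.3 and 9.4:

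1. Require the SAP, and all clinical, deviation-based and event-based PK exclusions (including those under Appendix 2 and SAP 6.3), to be signed before concentrations are released to the Clinical Facility.
2. Apply the remaining concentration-dependent criteria afterwards (pre-dose above 5% of Cmax; valid primary endpoints for both treatments), strictly by a rule written in advance and without discretion. Masking cannot be relied on here, because participant plus period reveals treatment to an open-label site.
3. Keep the sentence that the statistics start only after code receipt, and add that they also wait for database lock with the SAP and PK set signed.

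The cost is wording, sign-offs moved earlier and perhaps a few days before release. No participants, samples or staff are added. The numbers stay at 38 evaluable of 48 and 22 evaluable of 34, and power is unchanged.
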